6.4 Interim Analysis

RGF will be considered for early stopping for futility at 12-week intervals. RGF will not be considered for early stopping for success. Details of the interim analysis schedule, the futility stopping rule, and documentation of operating characteristics under a range of scenarios, are provided in the MPRDR (Appendix 1 of the M-SAP).

6.5 Secondary Efficacy Analyses

6.5.1 Hierarchical Testing

Principal inference for secondary efficacy endpoints will be based on comparison of the ABBV-CLS-7262 120 mg dosage vs. placebo in the ECC analysis set using a repeated-measures linear mixed model for the following endpoints (see Section 6.5.2 below). The default sequence for testing is the following:

- 1. Change from baseline to Week 24 in ALSFRS-R total score in the ECC analysis set,
- Change from baseline to Week 24 in respiratory function as assessed by slow vital capacity (SVC) and measured as percent predicted using GLI normal values in the ECC analysis set.
- Change from baseline to Week 24 in upper limb muscle strength as assessed
 isometrically using HHD and grip strength and measured as average percent change from
 baseline among maneuvers with non-zero strength at baseline in the ECC analysis set,
- Change from baseline to Week 24 in log-transformed serum NfL in the ECC analysis set, and
- 5. Change from baseline to Week 24 in ALSAQ-40 ADL domain score in the ECC analysis set.

If the primary analysis indicates a significant slowing in disease progression from the Bayesian shared-parameter model of function and survival, then each secondary efficacy endpoint would be declared significant in the specified sequence using a criterion of two-sided alpha of 0.05. After the first failure to declare significance, no endpoints lower in the hierarchy can be

significant. Nominal comparison-wise p-values for secondary efficacy endpoints will also be reported.

where id is a participant study identifier, trtrnd is the randomly assigned treatment group, visit is the visit identifier, Delta is change from baseline of the efficacy endpoint being tested for a given participant at a given visit, baseval is the baseline value of the efficacy endpoint, sx2bl is months since ALS symptom onset, dFRS is pre-baseline slope, nfl is baseline log-transformed serum NfL level, rlz is an indicator of riluzole use at baseline, edv is an indicator of edaravone use at baseline, and amx is an indicator of sodium phenylbutyrate/taurursodiol use at baseline.

Primary inference will be based on analysis of the ECC analysis set. Results from the FAS, ERO, ECM, and EPP analysis sets will be interpreted as sensitivity analyses. The following endpoints are added for analysis by this model in the ECC, FAS, and ERO analysis sets: ALSAQ-40 domain scores and overall symptom index, CNS-BFS total score, ROADS total score, and CSF NfL concentration. Only ALSFRS-R total score, HHD upper extremity percentage, and SVC will be analyzed in the ECM and EPP analysis sets. The model terms are expanded to include two active treatment groups, ABBV-CLS-7262 120 mg and 240 mg, and their interactions with visit. Primary inference will be based on comparison of the ABBV-CLS-7262 120 mg dosage vs. placebo.

The following SAS code specifies the primary linear contrast for an endpoint measured every 8 weeks assuming that the sort order for treatment group is placebo, ABBV-CLS-7262 120 mg, and ABBV-CLS-7262 240 mg and that visits are sorted chronologically:

```
estimate "3|120 vs PB0|dWk 24" trtrnd*visit 0 0 -1 0 0 1 0 0 0 / cl;
```

The estimand estimated by the primary linear contrast of the repeated-measures linear mixed model is the mean difference in 24-week change from baseline of a given continuous efficacy endpoint in the ABBV-CLS-7262 120 mg treatment group relative to the placebo group in the ECC population. The estimand is defined by the following attributes:

- Treatment: ABBV-CLS-7262 120 mg treatment vs. placebo.
- Population: ECC set as defined in Section 6.1.
- Variables: absolute change in endpoint from baseline to the Week 24 Visit.
- Intercurrent event: treatment discontinuation: handled via treatment policy approach, all data
 will be used including data collected during the placebo-controlled period after treatment
 discontinuation. Missing data post-treatment, including data missing due to death, will not be
 imputed and will be handled via missing at random assumption implemented through
 MMRM framework.
- Population-level summary: difference in conditional means of active treatment relative to placebo.

A nominally significant difference in 24-week change from baseline in the direction of greater improvement or less worsening among participants randomized to ABBV-CLS-7262 120 mg treatment would support inference of benefit from ABBV-CLS-7262 for the efficacy endpoint being tested. Inference from this analysis is supportive of inference from the Bayesian shared-parameter, repeated-measures model for the primary endpoint.

6.5.3 Random-slopes Model

The specification of the random-slopes model is the same as described in the M-SAP with the following modifications. The following endpoints are added for analysis by this model in the ECC, FAS, and ERO analysis sets: ALSAQ-40 domain scores and overall symptom index, CNS-BFS total score, ROADS total score, quantitative voice characteristics, and log-transformed CSF NfL concentration. Only ALSFRS-R total score, HHD upper extremity percentage, and SVC will be analyzed in the ECM and EPP analysis sets. The model terms are expanded to include the baseline value of a given efficacy endpoint and its interaction with month since baseline is added as an additional covariate and to include two active treatment groups, ABBV-CLS-7262 120 mg

and 240 mg, and their interactions with month. Principal inference will be based on comparison of the ABBV-CLS-7262 120 mg dosage vs. placebo. Satterthwaite's approximation will be used to estimate denominator degrees of freedom.

The following SAS code specifies the model:

where month is time in months from the Baseline Visit (assuming 12 months in an average of 365.25 days per year) and other fields are the same as identified above in Section 6.5.2.

The following SAS code specifies the primary linear contrast assuming that the sort order for treatment group is placebo, ABBV-CLS-7262 120 mg, and ABBV-CLS-7262 240 mg:

```
estimate "3|120 vs PBO|Slope (/mn)" month 0 trtrnd*month -1 1 0 / cl;
```

The estimand estimated by the primary linear contrast of the random-slopes model is the difference in mean rate of change from baseline to the Week 24 visit of a given continuous efficacy endpoint in the ABBV-CLS-7262 120 mg treatment group relative to the placebo group in the ECC population. The estimand is defined by the following attributes:

- Treatment: ABBV-CLS-7262 120 mg treatment vs. placebo.
- Population: ECC population as defined in Section 6.1.
- Variables: rate of change in endpoint from baseline to the Week 24 Visit.
- Intercurrent event: treatment discontinuation: handled via treatment policy approach, all data
 will be used including data collected during the placebo-controlled period after treatment
 discontinuation. Missing data post-treatment, including data missing due to death, will not be
 imputed and will be handled via missing at random assumption implemented through the
 random-slopes model.
- Population-level summary: difference in rate of change of active treatment relative to placebo.

A nominally significant difference in slopes in the direction of greater improvement or less worsening among participants randomized to ABBV-CLS-7262 120 mg treatment would support inference of benefit from ABBV-CLS-7262 for the efficacy endpoint being tested. Inference from this analysis is supportive of inference from the Bayesian shared-parameter, repeated-measures model for the primary endpoint.

6.5.4 Time-to-event Endpoints

The specification of survival analyses is the same as described in the M-SAP with the following modifications. Principal inference will be based on analysis of the ECC analysis set. Inference from analysis of time to the composite survival endpoint of death or death equivalent to the Week 24 time point is supportive of inference from the Bayesian shared-parameter, repeated-

measures model for the primary endpoint. Results from analysis of time to death or death equivalent in the FAS, ERO, ECM, and EPP analysis sets will be interpreted as sensitivity analyses. Only death/death-equivalent and death-alone will be analyzed in the ECM and EPP analysis sets. The time-to-event endpoints for clinical events will be analyzed in the FAS, ECC, and ERO analysis sets. Right-censored clinical events will be summarized by the same methods and analyzed by the same set of models as are specified for survival endpoints. Interval-censored clinical events will be analyzed using interval-censored methods. The model terms are expanded to include two active treatment groups, ABBV-CLS-7262 120 mg and 240 mg. Principal inference will be based on comparison of the ABBV-CLS-7262 120 mg dosage vs. placebo. For right-censored endpoints, summaries will include treatment-specific counts of the cumulative number of participants with events and the number of participants at risk for a first event at baseline, 8, 16, and 24 weeks after baseline, and inclusive of all RCT follow-up. For interval censored endpoints, summaries will include the number of participants at risk at baseline and the number of participants left censored, interval censored, and right censored at the end of RCT follow-up. Summaries will include treatment-specific times to 10%, 25%, and 50% percentiles of the estimated survival curves.

6.5.5 CAFS

The specification of CAFS analyses is the same as described in the M-SAP with the following modification. Ranking by ALSFRS-R total score and death/death-equivalent is added for analysis by this model in the ECC, FAS, and ERO analysis sets at the RCT Week 24 time point. Functional endpoints for analysis at the RCT Week 24 time point will include ALSFRS-R total score, HHD upper extremity percentage, and SVC. Only ALSFRS-R total score with death/death-equivalent will be analyzed in the ECM and EPP analysis sets. The CAFS analysis of ALSFRS-R total score and death/death-equivalent at the RCT Week 24 time point in the ECC analysis set with adjustment for time from symptom onset, delta-FRS, baseline use of edaravone, baseline use of riluzole, baseline use of sodium phenylbutyrate/taurursodiol, and baseline log-transformed serum NfL is a key sensitivity analysis of the primary Bayesian shared-parameter model.

6.5.6 Quantitative Voice Measures

Given the high frequency of voice recordings, a repeated-measures analysis with unstructured covariance is overly flexible but the assumption of linear change required by the random-slopes model may be overly rigid. To complement estimates from the random-slopes linear mixed model, quantitative voice characteristics will be analyzed in a linear mixed model in which the temporal profile for both fixed and random terms is modeled using partial linear B-splines with knots at 4, 8, and 16 weeks. The model will include fixed terms for B-splines, treatment group, treatment group × B-spline interaction and time since symptom onset, delta-FRS, baseline use of edaravone, baseline use of riluzole, baseline use of sodium phenylbutyrate/taurursodiol, and baseline log-transformed serum NfL and their interactions with the B-splines. In analyses of phonation time, age and height will be added as covariates. Covariates will be centered at their means. Articulatory precision will be cube-root transformed (transformed value = sign(original value) * abs(original value)^(1/3)) prior to analysis, and estimates and their 95% confidence bounds will be back-transformed (transformed estimate = (original estimate)^3).

The model will include random regimen-specific intercepts and slopes with unstructured covariance, random participant-specific B-splines with unstructured covariance, and a first-order

autoregressive structure for residuals. A simplified covariance structure assuming no regimenlevel covariance, heterogeneous compound symmetric covariance among the random B-splines, conditional independence of residuals, or a combination of the three simplifying assumptions will be used if the full model fails to converge.

The principal estimate will be the difference between ABBV-CLS-7262 120 mg vs. placebo in 24-week change from baseline. The estimate and its 95% Wald confidence bounds will be obtained by a linear contrast of adjusted means.

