4.3 Exploratory Endpoints

Change from baseline to Week 24 of following exploratory endpoints will be evaluated:

- Muscle strength: HHD lower extremity percentage, HHD global percentage,
- Biofluid biomarkers of neurodegeneration, ALS disease, and the ISR pathway, including: plasma and cerebrospinal fluid (CSF) NfL, serum creatinine, urinary p75^{ECD} (normalized to urinary creatinine), CSF GDF-15, CSF FGF21
- Patient-reported outcomes: ALSAQ-40 physical mobility, eating and drinking, communications, and emotional reactions domain scores and total score, CNS-BFS total score, ROADS total score,
- ALSFRS-R: bulbar, fine motor, gross motor, fine and gross motor combined, and respiratory domain scores,
- King's ALS Clinical Staging System stage and,
- Quantitative voice characteristics: maximum phonation time, pause rate, breathy vocal
 quality, pitch instability, regulation of voicing, articulatory precision, speaking rate,
 articulation rate, and monotonicity.

Change of secondary and exploratory endpoints from baseline to other time points and average rates of change from baseline to Week 24 will also be estimated in the ECC and ERO analysis sets (see Section 6.1 Analysis sets below for definitions).

The following exploratory time-to-event endpoints will be evaluated:

Time to clinical events: first hospitalization due to a serious adverse event (SAE), first
hospitalization due to an ALS-related SAE, first use of assisted ventilation, first placement of
a feeding tube, first time reaching King's stage 4a or 4b, death or death equivalent, death
alone.

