5.4 Biofluid Biomarkers

The definition and quantitation of serum NfL and serum creatinine are the same as described in the M-SAP with the following modifications. Serum NfL concentrations will be estimated from baseline serum samples twice. The first analysis of baseline serum samples for quantitation of serum NfL will be completed late enough to include baseline serum samples from all participants who will be included in the primary efficacy analysis for RGF and early enough that results from that analysis will be available at the time of database lock for clinical data from the 24-week placebo-controlled period. Serum NfL concentrations estimated from this first analysis will only be used as a covariate in analyses that include baseline serum NfL as a covariate. The second analysis of baseline serum samples for quantitation of serum NfL will be completed in combination with all other available serum samples collected during the 24-week placebocontrolled follow-up of participants who will be included in the primary efficacy analysis for RGF. All samples from a given participant in this second analysis will be analyzed on a single plate to minimize potential batch effect and serum NfL concentrations estimated from this second analysis will be used to estimate longitudinal changes in serum NfL as an efficacy endpoint. If baseline serum NfL concentrations for a given sample are not the same between the two analyses, they will be handled separately based on the above descriptions.

The following regimen-specific biomarkers will be assayed: plasma NfL, CSF NfL, CSF GDF-15, CSF FGF21, and urinary p75^{ECD}. Plasma NfL, CSF NfL, CSF GDF-15, and CSF FGF21 will be quantified by automated chemiluminescent enzyme immunoassay (LUMIPULSE G System, Fujirebio, Malvern, PA). Urinary p75^{ECD} will be assayed following Shepheard et al. (2022). Concentrations will be normalized to urinary creatinine concentration measured in the same sample and expressed as ng p75^{ECD} per mg creatinine. Following Shepheard et al. (2022), urinary p75^{ECD} from samples with urinary creatinine less than 0.3 ng/mL or greater than 3.0 ng/mL will be excluded from analysis.

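### Two rules for exploratory endpoints do not work as written: SAP 6.5.6 cubes a between-arm contrast, and SAP 5.4 sets urinary creatinine limits in ng/mL

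*SAP*

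**What the plan says.** **Articulatory precision.** SAP 6.5.6 gives the forward transform: "Articulatory precision will be cube-root transformed (transformed value = sign(original value) * abs(original value)^(1/3)) prior to analysis". It continues that "estimates and their 95% confidence bounds will be back-transformed (transformed estimate = (original estimate)^3". Later in the same section: "The principal estimate will be the difference between ABBV-CLS-7262 120 mg vs. placebo in 24-week change from baseline", and "The estimate and its 95% Wald confidence bounds will be obtained by a linear contrast of adjusted means". No sentence restricts the cube to arm-level means.

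**Urinary p75ECD.** SAP 5.4 expresses the result as nanograms of p75ECD "per mg creatinine". Citing a published assay paper, it then says that "samples with urinary creatinine less than 0.3 ng/mL or greater than 3.0 ng/mL will be excluded from analysis".

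**Status.** Both are exploratory in SAP 4.3. Articulatory precision is one of nine voice measures listed there ("pitch instability, regulation of voicing, articulatory precision, speaking rate"). Voice measures are also analysed by random slopes in SAP 6.5.3 ("ROADS total score, quantitative voice characteristics, and log-transformed CSF NfL concentration"). Neither endpoint is in the five-step sequence of SAP 6.5.1.

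**The concern.** Cubing undoes the cube root for a single value or for an arm's centre at one visit. It does not do so for a difference between two such values. The principal estimate in 6.5.6 is a difference between arms in a change over time, and it is the only quantity there with defined 95% bounds. A programmer following the text would cube it and report a number that looks like an original-scale effect but is not one.

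The creatinine limits are in nanograms per mL while the normalisation is per milligram, a factor of 1,000,000 apart. Applied literally, the exclusion could leave urinary p75ECD with no evaluable samples.

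At stake are one reported effect size with its interval, and one biomarker endpoint.

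**Working it through.** **(a) Back-transform**

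The plan gives no scale, centre, effect size or standard error for articulatory precision, so there is no figure of its own to reproduce. The inputs below, other than the transform, are assumptions.

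1. The round trip works for single values: -8, -1, 0.5 and 27 all return unchanged after cube root and cube.
2. Let a and p be the active and placebo centres at Week 24 on the cube-root scale, with a common baseline assumed, so the contrast of changes is d = a - p. The SAP rule reports d³. The difference of back-transformed centres is a³ - p³ = d³ + 3apd. The two agree only if d = 0, a = 0 or p = 0.
3. Take the placebo centre L on the original scale as -0.2 to -2, with p = ∛L and a = p + d.

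| d | Reported, d³ | a³ - p³ at L = -0.2 | L = -0.5 | L = -1 | L = -2 | Understatement |
|---|---|---|---|---|---|---|
| 0.10 | 0.001 | 0.086 | 0.166 | 0.271 | 0.439 | 86- to 439-fold |
| 0.20 | 0.008 | 0.143 | 0.291 | 0.488 | 0.809 | 18- to 101-fold |
| 0.50 | 0.125 | 0.199 | 0.475 | 0.875 | 1.561 | 1.6- to 12.5-fold |

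   Example, d = 0.10 and L = -0.2: p = -0.585, a = -0.485, so 0.001 + 3 × 0.485 × 0.585 × 0.10 = 0.086.

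4. The error can go the other way. With arms at 0.2 and -0.2, (∛0.2 - ∛(-0.2))³ = 8 × 0.2 = 1.6, against a difference of 0.4: a 4-fold overstatement.
5. Bounds, with d = 0.10 and an assumed SE of 0.04: the cube-root interval is 0.10 ± 1.96 × 0.04 = 0.022 to 0.178. Cubed, it becomes 0.00001 to 0.0057. Holding the placebo centre fixed at L = -1, the original-scale bounds are 0.063 to 0.445. Both intervals exclude zero, as they must, because cubing is monotone and maps 0 to 0.

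**(b) Creatinine limits**

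1. From the units alone: 1 mg = 1,000,000 ng. At 3.0 ng/mL, 1 mg of creatinine needs 1,000,000 / 3.0 = 333,333 mL, about 333 L of urine. At 0.3 ng/mL it needs about 3,333 L.
2. The documents give no urinary creatinine values. Assume 0.01 to 5 mg/mL, which is 10,000 to 5,000,000 ng/mL. Dividing by the upper limit of 3.0 gives 3,333 to 1,666,667. Every sample in that range is excluded.
3. If the limits were in mg/mL, assumed values from 0.3 to 3 would be kept, and 0.05, 0.1, 4 and 5 would be excluded. That would be a working filter, but the unit is an inference.

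**The case against.** **The cube may be meant for adjusted means.** The sentence is plural and sits with the model terms, before the principal estimate is defined; for an adjusted mean at one visit the rule is valid. That last point stands, but the restriction is not written, and the contrast is later described in nearly the same terms, as an estimate with 95% bounds. Cubing arm-level changes would also fail, since each is itself a difference between visits.

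**Untransformed summaries are planned.** SAP 3.4 keeps descriptive summaries on the original scale, so readers will have raw figures to compare. This is a real safeguard against being misled, but it does not repair the adjusted estimate or its interval.

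**The fold-errors depend on chosen inputs.** This stands. With d = 0.50 and a placebo centre of -0.01, p = -0.215 and a = 0.285, so a³ - p³ = 0.033 against a reported 0.125: about 3.8-fold overstatement. The model also does not force equal baselines. Only the algebra comes from the documents; the unpredictable direction means a reader cannot correct the reported figure.

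**The creatinine unit may be a slip that shows itself.** It turns on one letter, may be a misreading of the page, and a rule that drops every sample would be noticed at programming. However, the same unit appears at both limits, and changing a prespecified exclusion after data are seen is a post hoc change. A unit different from the normalisation is not in itself a contradiction, and that all samples are lost rests on the assumed range.

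**Conclusion.** Both rules are wrong as written. In 6.5.6, the size and bounds reported for the articulatory precision contrast would not be a difference on the original scale. This follows from the SAP text and algebra; the fold-errors are illustrations under assumed centres and contrasts, and can run in either direction. Sign and exclusion of zero are preserved.

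In 5.4, the limits as printed would remove every urinary p75ECD sample over an assumed 0.01 to 5 mg/mL of creatinine. The intended unit is not stated and could not be checked against the cited paper.

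Importance is low to moderate: each part touches one exploratory endpoint. The primary analysis, the secondary hierarchy, power and type I error are unaffected. The changes should still be made because they are cheap and need to precede data lock.

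**What to change.** **SAP 6.5.6.** Choose one and state it:

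- Report the between-arm contrast and its interval on the cube-root scale, without cubing.
- Cube each arm's adjusted baseline and Week 24 means, form the contrast from those, and obtain bounds by the delta method or bootstrap. Label it a difference of back-transformed means, not of arithmetic means.

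In either case, say that the cube applies only to arm-level means at a visit, never to changes or contrasts.

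**SAP 5.4.** Check the unit of the 0.3 and 3.0 limits against the cited assay source and correct it. It is probably mg/mL, in keeping with the per-mg normalisation, but this needs confirmation.

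The cost is one sentence in each section and trivial programming. SAP 3.4 already provides for updates on transformations before regimen data lock.
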